## I. Background

There is an urgent need for effective interventions to prevent and treat COVID-19. Vitamin D deficiency has recently been identified as potentially contributing to the spread of COVID-19 and vitamin D supplementation has been identified as having potential in prevention and treatment. There is evidence that vitamin D can prevent or improve outcomes in many infectious and inflammatory conditions, including acute and chronic respiratory infections, and an increasing understanding of its immunomodulatory and anti-inflammatory functions. A recent meta-analysis found a 70% reduction in viral respiratory tract infections among persons with vitamin D deficiency randomized to vitamin D treatment. The potential importance of vitamin D in the spread of COVID is supported by the fact that nearly half the US population is vitamin D deficient, with higher rates among persons with darker skin and/or lower sun exposure, including those living in higher latitudes in the winter, nursing home residents and health care workers, who also have greater risk of COVID-19. In contrast, populations with greater vitamin D intake, including pregnant women, children and persons who eat more fish, have lower rates of COVID-19. Also, we have recently analyzed internal data at the University of Chicago Medicine and found that the risk of testing positive for COVID-19 is 77% higher for vitamin D deficient persons who are not treated.

Though these findings are suggestive, experimental studies are needed to establish if vitamin D treatment can decrease the risk or improve outcomes of COVID-19. Such data are especially important because efforts to treat some infectious or inflammatory conditions with vitamin D have not been successful. Negative findings have been attributed to vitamin D dosages that are too low, infrequent, or fail to account for baseline vitamin D levels, dietary sources or sun exposure. Dose is very important; the recommended daily allowance (RDA) of 600 IU/day and definition of sufficient level ( $\geq 30$  ng/ml) are based on effects on bone health, not immune function, for which needs are not known. The Institute of Medicine (IOM) has recommended 4,000 IU/day as safe for regular consumption but did not recommend higher doses based on the lack of clear evidence of benefit for higher doses and some evidence of possible toxicity, especially hypercalcemia and resulting falls in older persons. However, humans evolved under conditions of sun exposure that would produce 10,000-25,000 IU/day – far more than recommended by the IOM, and lifeguards have vitamin D levels of 50-100 ng/ml. Moreover, large case series have found low rates of side effects (e.g., hypercalcemia) with doses as high as 10,000 IU/day. Experimental studies to define ideal vitamin D dosing are justified in populations with different needs for, risks of, and preferences related to vitamin D treatment. Randomizing subjects to a minimal dose of vitamin D (e.g., 400 IU/day) or a high dose (e.g., 10,000 IU/day) might seem to maximize statistical power to assess the effectiveness of vitamin D in COVID-19. However, some potential research subjects may consider the high dose to carry unnecessary risks, so we propose offering subjects the option to be randomized to moderate dose, 4,000 IU/day, if they are not comfortable to maximize participation.

In this context, *the proposed study is innovative most importantly because it proposes to perform a randomized clinical trial to prevent COVID-19.*

## II. Purpose

We propose to seek to recruit participants to be randomized to low versus high (10,000 IU/day) or low versus moderate (4,000 IU/day) dose vitamin D and pool these populations for our primary analyses. The study will focus on health care workers and other individuals from Chicagoland communities with elevated risk of exposure to COVID-19. In addition to their high exposure rates to COVID-19, focusing on health care workers is also useful because they have high rates of vitamin D deficiency due to indoor work and long hours, are likely to tolerate high doses of vitamin D given their generally good health, and have ready access to monitoring for dose toxicity. In addition to HCWs, we have decided to expand our focus to include other adults in Chicagoland communities. Due to vaccine distribution in the coming months prioritizing HCWs, we want to offer the potential benefits of vitamin D in COVID-19 prevention to those who will not have prioritized access to vaccines, or choose to be vaccinated at present. **Thus, our overall aim is to compare the risks of COVID-19 in health care workers and other Chicagoland adults at increased risk of COVID-19 randomized to low (400 IU/day) vs. moderate (4,000 IU/day) or high (10,000 IU/day) dose vitamin D. Our specific aims are:**

**Aim 1:** To compare the risk of developing COVID-19 in health care workers and other Chicagoland community members at increased risk of COVID-19 randomized to low vs. moderate or high dose vitamin D. We hypothesize that moderate and high dose therapy will reduce rates of COVID-19 compared to low dose therapy because vitamin D will reduce symptomatic infection that prompts testing for COVID-19. Our primary analysis will pool subjects randomized to the moderate or high dose and compare them to low dose subjects, with secondary analyses comparing low to moderate and low to high. The design thus seeks to maximize potential to find statistically significant results between different dosages given uncertainty in subject willingness to be randomized to different doses.

**Aim 2:** To compare COVID-19 seroconversion in health care workers and other Chicagoland community members at increased risk of COVID-19 randomized to low vs. moderate or high dose vitamin D. As we suspect the main effect of vitamin D may be to decrease symptomatic disease we hypothesize that there may be little or no difference in seroconversion.

**Aim 3:** To compare COVID-19 outcomes (hospitalization, ICU stay, ventilator use, death) in health care workers and other Chicagoland community members at increased risk of COVID-19 randomized to low vs. moderate or high dose vitamin D. Consistent with several recent observational analyses, we expect higher doses to improve COVID-19 outcomes.

Comparing the effectiveness of low to moderate and high dose vitamin D dosing strategies for COVID-19 is important and innovative given the global impact of COVID-19 and need for studies that examine the effects of higher doses of vitamin D and the focus on higher risk HCWs and other individuals in high-density, racially diverse metropolitan areas, both groups which already have increased risk relative to the general population.

We are additionally interested in the relationship between vitamin A and vitamin D, and how they impact immune response in the context of COVID-19. Therefore, we are adding additional Aims 4-6.

**Aim 4: Create a biobank of PBMCs from a panel of 500 individuals with well characterized levels of vitamin A and D.** We propose to cryopreserve PBMCs derived from ~20 ml of blood to test the impact of vitamin A and D levels in the regulation of immune responses. PBMCs will be used as described in Aims 2 and 3 below. In addition, and upon the availability of additional funds, we will collect genetic data from all individuals to test for the impact of genetics to inter-individual differences in immune response and its interaction with vitamin A and D levels.

**Aim 5: Evaluate the impact of vitamin A and D levels on immune function.** We will perform immunophenotyping of PBMC using a panel of 30 antibodies that allow characterizing the different immune cell populations found in circulation, as well as their functional status. Using these data we will ask if

there is an association between the prevalence of certain immune cell population or functional potential and vitamin A and D levels.

**Aim 6: Evaluate the impact of vitamin A and D levels on PBMC gene expression levels.** We will perform transcriptional profiling of PBMC from a panel of 100 individuals enriched for individuals on the two extremes of the distributions of vitamin A and D levels. These data will be used to identify changes in gene expression levels that differ between individuals showing low- vs high-vitamin A/D levels.

### **Other protocol linkages**

#### Linkage to protocol # 20-2183:

Protocol 20-2183 will use existing samples drawn under this protocol (further described in Section III) to analyze the following aims:

**Aim 7:** To test the hypothesis that oral vitamin D3 intervention will inhibit the renin- angiotensin system and reduce the incidence and/or severity of COVID-19 infections. A dose response will be tested in this study by comparing 400 IU to 4,000 IU to 10,000 IU vitmin D3.

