## III. Description of protocol methodology

### **Summary**

To meet our aims, we propose a 2,000-person two-arm, double-blinded randomized controlled trial in HCWs and other Chicagoland community adults at University of Chicago Medicine (UCM) and Rush University (RU) selected to ensure safe administration of low compared to moderate or high dose vitamin D that will randomize half the subjects to low dose vitamin D therapy (400 IU/day) and half to moderate (4,000 IU/day) or high (10,000 IU/day).

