During the consent process, study participants will be able to choose between being randomized between the low versus high dose strategy or the low dose versus moderate dose strategy. Moderate and high dose treatment participants will be combined for analysis as described below. The moderate and high treatment doses were chosen with help from our clinical advisory committee because they are generally considered safe and potentially effective among persons who meet our inclusion criteria based on medical history and baseline laboratory values (normal calcium and PTH, and negative COVID-19 antibodies). The low dose was selected to ensure that all subjects had a high likelihood of a total vitamin D intake that met the recommended daily allowance (RDA). All patients will be informed of whether their baseline calcium and PTH are normal. Patients who are still eligible for study participation after initial testing will be asked prior to randomization whether they are still willing to participate to maximize retention and minimize dropout. After randomization, subjects will be instructed to pick up their 9-month supply of vitamin D at either UCMC or Rush University corresponding to their randomized, blinded dose. For those unable to pick up their bottles in-person, the UCM IDS pharmacy will mail the subject their bottle. We propose a 3 to 9-month study period, depending on when the subject was recruited, as described in the study timeline of Section IV. Subjects recruited after September 30th will participate in the intervention 6 months to align with study timeline and funding. Subjects enrolled between January 1, 2023 and March 31, 2023 will take the study drug until June 2023, so at least 3 and no more than 6 months. Chart review for subjects will occur for 12 months after the active intervention period has ended. This study timeline is further detailed in Tables 1-4 of Section IV in the currently approved protocol document. Adverse events, defined as hypercalcemia or unexplained increased falls in either study arm will prompt discontinuation of the study medication and further evaluation as reported in the monitoring section below.

[figure not shown]
On the advice of our Clinical Advisory Council faculty members, patients who test for PTH >85pg/dL but have calcium levels <10mg/dL and low vitamin D (<30ng/mL) will be eligible to continue in the study because those

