8. Report already taking more than 400 IU of vitamin D daily as recommended by their health care provider, excluding multivitamins and excluding supplements that include vitamin D and calcium together, unless permission is received from the prescribing health care provider to participate. In this case, no more than 1,000 IU vitamin D may be taken daily in addition to the study medication and we would limit the subjects to participation in the low vs. moderate arm of the study, producing a maximum dose of 5,000 IU per day. We note that the NAM recommended a maximum dose of 4,000 IU per day without medical supervision based on evidence that 5,000 was safe and known uncertainty about the precision of dosing in 5,000 IU supplements available over the counter. However, since we are testing the dosage of our 4,000 IU supplements to high precision and these patients would be taking their original supplements with a labelled dose of 1,000 IU or less, we think that the combination of our 4,000 IU supplements and the patient's original supplement of up to 1,000 IU should not provide a maximum dose meaningfully above the 5,000 IU actual dose the NAM has considered safe for taking without medical supervision. We note further that we are measuring vitamin D levels and PTH in these patients regardless in this study. We do, however, have another study of vitamin D and COVID (IRB# 20-0847), in which we are not measuring these levels, for which it is more important to not substantially exceed NAM maximum level of 5,000 IU per day. The approach described here allows us to align the approach in these two studies.
9. Report taking D2.
10. Report a history of sarcoidosis.

11. Screen positive for hypercalcemia ( at UCM, defined as >10.4 mg/dL and at Rush, defined as >11.2 mg/dL) during the initial blood test.
12. Screen positive for hyperparathyroidism (PTH>85 pg/dL) during the initial blood test with calcium  $\geq 10$ mg/dL and normal levels of vitamin D ( $\geq 30$ ng/mL)
13. Have vitamin D levels of >100ng/mL at study start, or >250ng/mL during follow-up labs.
14. Are unwilling to provide blood samples during quarterly blood tests.
15. Are unwilling to take daily vitamin D.

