For our primary outcome of COVID-19 infection as measured by patient report of clinically confirmed COVID-19 (or viral PCR when available) and secondary outcomes of COVID-19 antibody seroconversion and disease severity (hospitalization, ICU stay, ventilator use, death), hazard models will be employed to assess the effect of each vitamin D dosing strategy on the outcome. We will first develop hazard ratios for between-group analyses on the primary outcome using log-rank tests, and then develop Cox proportional hazard models to model the hazard function on a set of covariates including but not limited to, moderate or high vitamin D dose, baseline vitamin D levels, age, gender, race, ethnicity, sun exposure, sleep habits, exposure of cohabitants, job type, and study site. We will also control for randomization date to adjust the underlying hazard function for COVID-19 prevalence over time. While our primary analysis will pool subjects randomized to either the moderate or high dose and compare them to low dose subjects, we will also perform secondary analyses comparing low to moderate and low to high and additional analyses that use post randomization vitamin D levels as time varying covariates. The design thus seeks to maximize potential to find statistically significant results between different dosages given uncertainty in subject willingness to be randomized to different doses. As noted above, the sample size was chosen to have at least 80% power to detect a 25% or larger decrease in the hazard of developing COVID-19 between study arms at  $p<0.05$  assuming a 30% baseline 10-month COVID incidence over the study period, in line with the 3% monthly incidence cited above. As finding that a higher dose has no effect or a paradoxical adverse effect on COVID incidence would both lead to use of a lower dose given even the small risks of higher dose vitamin D, Ruxson and Neuhauser would argue for use of a 1-sided test, resulting in 80% power to detect a 20% or larger decrease.

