At the beginning of the consent process, subjects will be asked to verify their identity by emailing or texting the study email or study cell phone a photo of their diver's license, state ID, passport or employee ID. They will be asked for their email address where a signed copy of the consent form will be sent for their records. In the consent form, subjects will be informed about the nature of the intervention, that they will be receiving a daily dose of vitamin D, either low or moderate/high, and must self-administer this dose each day. They will be informed about the nature of the intervention, that they are blinded to the dose they receive. Subjects will be reminded that participation is entirely voluntary, and they may withdraw at any time without consequence. Subjects will also be informed about the data collection methods, including the survey and testing they will undergo at each stage, and that they will be informed about test results for COVID-19 antibodies only during the study period. They will be informed that their PTH, calcium and vitamin D results will be withheld until completion of study participation unless they suggest a safety concern. They will be educated about the risks of the study as described above in "Potential Risks". Subjects will be informed about what will be done if they are found to be hypercalcemic: First, they will be told to cease vitamin D supplementation. Subjects at UCM with a calcium level 10.5-12 mg/dL and at Rush with a calcium level 11.3-12mg/dL will be instructed to consult with their primary care physician. All subjects with a calcium level of 12.1-14 mg/dL will be referred to urgent care. All subjects with a calcium level greater than 14 mg/dL will be referred to the emergency room. These participants will continue to undergo monitoring blood draws and surveys and may resume vitamin D supplementation per study protocol with a physician note.

Subjects will then be instructed to select their randomization preference on the consent form. If a potential subject says they are already taking a supplement or supplements that contains 2,000IU or less of vitamin D in total, they may continue to take those supplements while part of the study, however, they will only be allowed to enroll in the arm that randomized them between 400 and 4,000IU.

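### Aim 7's three-dose comparison crosses two self-chosen randomization pairs, so it needs within-pair analysis and a non-randomized label for 4,000 vs 10,000 IU

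*Combined protocol and SAP*

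**What the plan says.** Aim 7 (Section II, linkage to protocol 20-2183) concerns inhibition of the renin-angiotensin system and COVID-19 incidence or severity. Its planned comparison is: "A dose response will be tested in this study by comparing 400 IU to 4,000 IU to 10,000 IU vitmin D3". The analysis is assigned to a linked protocol: "Protocol 20-2183 will use existing samples drawn under this protocol".

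The randomization that Aim 7 relies on is set out in Section III, Summary: "study participants will be able to choose between being randomized between the low versus high dose strategy or the low dose versus moderate dose strategy". Section I gives the reason for offering a choice, namely that "some potential research subjects may consider the high dose to carry unnecessary risks".

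Two places restrict the choice for supplement users. Section VIII, exclusion criterion 8, covers people on provider-recommended vitamin D who are admitted with permission: "we would limit the subjects to participation in the low vs. moderate arm of the study". Section XIV covers people who continue their own supplements: "they will only be allowed to enroll in the arm that randomized them between 400 and 4,000IU". The two places give different ceilings for continued intake (1,000 IU and 2,000 IU a day). They need to be reconciled, because the ceiling helps decide who is confined to one pair.

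Section IX pools moderate and high dose for the primary analysis and adds that "we will also perform secondary analyses comparing low to moderate and low to high". It does not say that the low-dose comparators come from the same pair. Its covariate list is open-ended and includes baseline vitamin D level, but names neither the chosen pair nor baseline supplement use. Supplement doses are recorded in the intake survey (Section III, Procedures and Materials).

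**The concern.** What separates a dose response from a finding that any higher dose differs from low dose is the step from 4,000 to 10,000 IU. No participant is randomized across that step. The two active groups come from populations that sorted themselves by comfort with the high dose and, by rule, by continued supplement use. The supplement rule acts on vitamin D intake, the exposure under study.

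If the two populations differ in their risk of COVID-19, that difference can appear as a dose trend or hide a real one. Aim 7 could then report a dose response, or its absence, that randomization does not support.

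**Working it through.** **No stated figure to reproduce.** The documents give no sample size or power for Aim 7 or for any 4,000-vs-10,000 IU comparison. What follows is an illustration.

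**Inputs.** From the documents: 2,000 participants, half on low dose, and 30% incidence over the study period (Sections VII and VIII). Assumed: half choose each pair, allocation is 1:1 within each pair, and the high-pair choosers have lower baseline risk. N = 1,000 is also tried, because the extra Aim 7 intake laboratory tests are limited to UCM participants; that count is an assumption.

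**Step 1. Apparent effects when vitamin D does nothing.** Let risk be 30% in the low-vs-moderate pair and 25% in the low-vs-high pair, whatever the dose.
- Pooled 400 IU risk: (0.30 + 0.25)/2 = 0.275.
- 4,000 vs pooled 400 IU: 0.30/0.275 = 1.09.
- 10,000 vs pooled 400 IU: 0.25/0.275 = 0.91.
- 10,000 vs 4,000 IU: 0.25/0.30 = 0.83.
- Within each pair: 0.30/0.30 = 0.25/0.25 = 1.00.

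**Step 2. False-positive rate of an unstratified trend.** Use a score test with dose scores s = 0.4, 4 and 10 and group sizes n = 1,000, 500 and 500.
- Mean score: (400 + 2,000 + 5,000)/2,000 = 3.7.
- Σn(s − 3.7)² = 10,890 + 45 + 19,845 = 30,780.
- Expected T = Σs(x − np) = 0.4(275 − 275) + 4(150 − 137.5) + 10(125 − 137.5) = −75.
- SD = √(0.275 × 0.725 × 30,780) = 78.3, so the expected z is −75/78.3 = −0.96.
- Probability of |z| > 1.96: about 16%. A simulation of 20,000 trials gave 15%.

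With 22.5% in the high pair, T = −112.5, SD = 77.2 and z = −1.46, giving 31% (simulation 31%). At N = 1,000 both z values shrink by √2, to 0.68 and 1.03, giving about 10% and 18%.

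**Step 3. The same in hazard ratios.** ln(0.75)/ln(0.70) = 0.81 and ln(0.775)/ln(0.70) = 0.71, so these risks correspond to chooser hazard ratios near 0.8 and 0.7. Two sets of simulated time-to-event trials with no vitamin D effect, differing slightly in how the 30% was anchored, gave:

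| Chooser hazard ratio | False trend, N = 1,000 | False trend, N = 2,000 | False 4,000-vs-10,000 difference, N = 1,000 | Same, N = 2,000 |
|---|---|---|---|---|
| 0.7 | 18–21% | 33–35% | 52–58% | 82–87% |
| 0.8 | 10% | 17% | 25–28% | 48–49% |
| 1.0 | about 5% | about 5% | about 5% | about 5% |

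**Step 4. Stratifying by pair.** With each active dose compared only with the 400 IU controls of its own pair, the trend test rejected in 4.8% to 5.3% of null trials. This covered 30%, 50% or 70% choosing the high pair, with high-pair risk of 30%, 25% or 22.5%.

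**Step 5. Precision of the indirect contrast.** The ratio of the two within-pair hazard ratios has SE(log ratio) ≈ √(Σ 1/events) over four cells. With equal pairs and 30% incidence:
- N = 2,000: 150 events per cell, √(4/150) = 0.163, 95% CI factor exp(1.96 × 0.163) = 1.4.
- N = 1,000: 75 events per cell, √(4/75) = 0.231, 95% CI factor exp(1.96 × 0.231) = 1.6.

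**The case against.** **The Aim 7 analysis belongs to protocol 20-2183, which is not supplied.** The sentence in this protocol does not call for pooled 400 IU controls, an unadjusted trend or a head-to-head test of the two higher doses. That is fair, and the linked protocol may already handle the matter. But the three-dose comparison is stated here and the randomization that limits it is defined here. Nothing in the supplied text specifies a within-pair analysis.

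**The percentages are hypothetical and unadjusted.** This stands. They depend on an assumed chooser hazard ratio, and at 1.0 nothing happens. Section IX already lists baseline vitamin D level, sun exposure, job type, cohabitant exposure, site and randomization date, and the list is open, so adjustment would probably remove part of any bias. The figures also cover incidence only, not the renin-angiotensin measures, and the N = 2,000 figures do not fit measurements limited to UCM participants.

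**Stronger readings a reader might infer, and why the documents do not support them.**
- *That supplement users are sent to 4,000 IU.* They are confined to a pair, and about half of them should receive 400 IU.
- *That the whole dose response is confounded and no trend test is acceptable.* The 400-vs-4,000 and 400-vs-10,000 IU contrasts are each randomized within their pair, and a pair-stratified trend test holds its error rate under the null.
- *That the trial needs a third consent option randomizing willing participants across all three doses.* The preference design is deliberate and explained. Such an option would change the dose mix in the pooled active arm and would need several consent forms amended late in recruitment.

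**Conclusion.** The point holds in a limited form. As written, Aim 7's comparison includes a step, 4,000 to 10,000 IU, that is not randomized. A trend test that pools the 400 IU groups without stratifying by pair shares the problem. The same ambiguity affects the secondary dose contrasts in Section IX, which do not say which low-dose participants are the comparators.

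Neither the size nor the direction of the bias can be derived from the documents. The 10% to 35% false-positive range for the trend rests on assumed chooser hazard ratios of 0.7 to 0.8, equal pairs, 30% incidence, N of 1,000 to 2,000 and no covariate adjustment.

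Stratifying removes the false trend but does not make 4,000 vs 10,000 IU a randomized comparison: a difference between the two within-pair effects may still reflect different populations. The pooled primary comparison is unaffected, given 1:1 allocation within each pair. This should be corrected, but it is a matter for a linked, non-primary aim and the secondary analyses.

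**What to change.** In the Aim 7 text, and likewise for the secondary dose contrasts in Section IX:

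1. Estimate 400 vs 4,000 IU and 400 vs 10,000 IU separately, each against the 400 IU controls of the same chosen pair.
2. Stratify any dose-trend test by chosen pair.
3. Adjust for baseline supplement intake, using the intake survey data.
4. Label any 4,000-vs-10,000 IU contrast, including the ratio of the two within-pair hazard ratios, as an indirect, non-randomized comparison that may reflect different populations.
5. If protocol 20-2183 already specifies this, add a cross-reference.

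The cost is wording plus one stratification variable, which the consent form already records. No extra participants, visits or measurements are needed. The statistical price is the wider interval for the indirect contrast shown in Step 5: the 95% limits lie a factor of about 1.4 (N = 2,000) to 1.6 (N = 1,000) either side of the estimate, and further if the pairs are unequal.
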